Wayfinding Intervention in High-Fidelity Long-Term
Memory December 8, 2022
NCT 04253587

Statistical Analysis Plan:

Analyses were conducted under the intent-to-treat (ITT) principle, and data from all participants randomized to begin a training arm were included in the analyses. Each cognitive outcome measure is independent from the others (i.e., each measure uses a compartmentalized procedure, unique stimuli, and different metrics) and was considered as a potential measure of generalization of training effects in its own right. Therefore, the analyses of LDI scores and WALK scores were independent of each other.

Mixed models ANOVA were employed to examine the differences across the two conditions (Trackers and Control) between T1 (baseline) and T2 (post-training). Data were analyzed and statistics calculated using IBM SPSS Statistics release 20.0, and the threshold of statistical significance for false positives was set at $p < 0.05$.

Research Protocol Summary

Title: Wayfinding Intervention in High-Fidelity Long-Term Memory

Rationale: Therapeutic interventions have not yet been shown to demonstrate restorative effects for declining long-term memory (LTM) that affects many healthy older adults. Our motivation was to demonstrate a cognitive intervention based on spatial wayfinding through unfamiliar surroundings that induced beneficial gains in untrained measures of high-fidelity LTM, which is the most precise form of LTM.

Goals: Spatial navigation tasks have been applied to achieve environmental enrichment in animals, which refers to exposure and learning that have been linked to the vitality of the memory system in the brain. Labyrinth is a virtual reality (VR) spatial wayfinding game that mimics this environmental enrichment approach with the goal of improving, and potentially restoring, memory abilities in healthy older adults. The primary objective is to show training-induced gains in high-fidelity LTM (i.e., mnemonic discrimination).

Design: All participants provided informed consent under UCSF IRB 19-27586.

Experiments enrolled 49 healthy older adults (mean 69 years of age) per protocol in a randomized controlled type interventional study. Outcome data were assessed at baseline (T1) and post-training timepoints (T2), and the primary outcome measures assessed two capabilities for high-fidelity LTM retrieval. The two treatment arms were Labyrinth VR training versus placebo control narrative games played on an iPad tablet computer. After orientation to their respective treatment games, all participants completed an expectancy survey regarding how their treatment would affect cognitive performance.

Methodology: Experiments used an HTC® VIVE™ VR system with the Unity cross-platform game engine (©Unity Technologies) to present our spatial wayfinding game. The cognitive intervention required approximately 12 hours game play of either Labyrinth VR treatment, or four commercially available narrative computer games as placebo controls, over four weeks.

MDT was one primary outcome measure and provided an LDI score for each participant at each timepoint in order to assess generalization of Labyrinth training to untrained capability for mnemonic discrimination as a measure of high-fidelity LTM. Mixed design ANOVA (repeated factors for time T1|T2 X between factors for condition Labyrinth-VR | Controls) was used for the analysis of LDI.

WALK was another primary outcome measure and provided an Items Recalled score for each participant at each timepoint in order to assess generalization of Labyrinth training to untrained capability for recent autobiographical memory as a measure of high-fidelity LTM. Mixed design ANOVA (repeated factors for time T1|T2 X between factors for condition Labyrinth-VR | Controls) was used for the analysis of Items Recalled.

Wayfinding Intervention in High-Fidelity Long-Term Memory

December 8, 2022

NCT 04253587

Statistical Analysis Plan:

Analyses were conducted under the intent-to-treat (ITT) principle, and data from all participants randomized to begin a training arm were included in the analyses. Each cognitive outcome measure is independent from the others (i.e., each measure uses a compartmentalized procedure, unique stimuli, and different metrics) and was considered as a potential measure of generalization of training effects in its own right. Therefore, the analyses of LDI scores and TOUR scores were independent of each other.

Mixed models ANOVA were employed to examine the differences across the two conditions (Trackers and Control) between T1 (baseline) and T2 (post-training). Data were analyzed and statistics calculated using IBM SPSS Statistics release 20.0, and the threshold of statistical significance for false positives was set at $p < 0.05$.

In consideration of a funding constraint, data were collected and analyzed only in the Experimental: LabyrinthVR Trackers and Placebo Comparator: Placebo Controls arms.

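### Does the T1–T2 mixed-design ANOVA undercut the intention-to-treat claim by dropping participants without a T2 score?

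*Combined protocol and SAP*

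**What the plan says.** The Statistical Analysis Plan, which is printed twice in the combined document, opens with "Analyses were conducted under the intent-to-treat (ITT) principle" and adds that "data from all participants randomized to begin a training arm were included in the analyses". Its second paragraph describes the model: "Mixed models ANOVA were employed to examine the differences across the two conditions (Trackers and Control) between T1 (baseline) and T2 (post-training"). The software is SPSS 20. Neither the procedure within it nor the estimation method is named, and no rule is given for a missing score.

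The Methodology section of the Research Protocol Summary is more specific. For the first primary outcome, "Mixed design ANOVA (repeated factors for time T1|T2 X between factors for condition Labyrinth-VR | Controls) was used for the analysis of LDI". The same design "was used for the analysis of Items Recalled", the second primary outcome.

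The same section has the only wording that bears on completeness. The MDT "provided an LDI score for each participant at each timepoint", and the WALK test "provided an Items Recalled score for each participant at each timepoint".

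The Design section gives 49 enrolled and two assessments, T1 and T2. It gives no arm sizes, number lost or number analysed. The text is in the past tense, so it describes an analysis already done.

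**The concern.** With one baseline and one follow-up score, the classical time-by-condition test is a two-sample t-test on the change T2 − T1. A participant without T2 has no change score and drops out of the test. An analysis described as including everyone randomized could therefore be a complete-case analysis.

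This matters if loss differs between arms and depends on the score. The arms ask different things of participants: about 12 hours of play over four weeks, in a VR headset or on a tablet. Unequal loss is therefore conceivable. If low scorers at baseline left the VR arm, regression to the mean would make VR look worse than it is; if high scorers left, better. A REML mixed model on all available scores would keep participants who have T1 only, and would remove this bias when loss depends on the observed baseline. It is available in the same software, so the plan seems to have passed over a safer method at no saving.

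**Working it through.** The documents contain no sample-size, power or dropout figure to reproduce. The check has three parts: whether the two methods differ, by how much if T2 is incomplete, and whether the documents show that it is.

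**Inputs.** From the documents: 49 participants, T1 and T2 only, threshold 0.05. Assumed: arms of 24 and 25, scores with SD 1, T1–T2 correlation ρ of 0.5, 0.6 or 0.7, and the loss rates below.

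**1. Complete T2.** The ANOVA interaction is (mean change in VR) − (mean change in controls), tested on 49 − 2 = 47 df. In one simulated data set with ρ = 0.6, the ANOVA and the REML fits with compound-symmetry and unstructured covariance all gave estimate 0.669 and t = 3.083. With ρ = 0.3 they all gave t = 1.504. The only discrepancy was a random-intercept model at ρ = −0.3 (t = 2.48 against 2.19), where the unstructured model still gave 2.19. So with complete T2 the choice changes nothing.

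**2. Incomplete T2, classical procedure.** Suppose that loss in the VR arm depends on baseline x through logit p(x) = c − x (low scorers leave) and that controls are lost at random. The completers' baseline mean in VR shifts by

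m = ∫x φ(x)(1 − p(x))dx ÷ ∫φ(x)(1 − p(x))dx,

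and the complete-case contrast is biased by −(1 − ρ)m. Setting c for 10% or 24% VR loss and integrating numerically gives m = 0.091 and 0.205.

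| Loss, VR / control | (1 − ρ)m at ρ = 0.5 / 0.6 / 0.7 | Simulated bias (SD), 40,000 trials per case |
|---|---|---|
| 0 / 0 | 0 | −0.003 / 0.000 / −0.002 |
| 12% / 12%, same mechanism | cancels | 0.000 / −0.002 / 0.000 |
| 10% / 5%, low scorers leave VR | 0.045 / 0.036 / 0.027 | −0.044 / −0.036 / −0.026 |
| 24% / 5%, low scorers leave VR | 0.103 / 0.082 / 0.062 | −0.100 / −0.084 / −0.059 |

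Formula and simulation agree in size. If high scorers leave instead, the sign reverses. In standard errors the bias is 0.11–0.15 at 10% / 5% and 0.25–0.33 at 24% / 5%.

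Consequences for the tests:

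- Two-sided size is 5.1–5.3% at 10% / 5% and 5.6–6.3% at 24% / 5%. The mixed model stays at 4.9–5.3%.
- The errors become lopsided. At 24% / 5% with high scorers lost, false positives favouring VR are 5.3 / 4.6 / 4.5% against a nominal 2.5%; the mixed model gives 2.8 / 2.7 / 2.8%. At ρ = 0.5, 6.3 − 5.3 = 1.0% still falls on the other side.
- For an effect with 80% power at complete T2, with low scorers lost at 24% / 5%, power is 61 / 62 / 64% for complete cases and 75 / 74 / 74% for the mixed model. At 10% / 5% it is 72 / 72 / 73% against 78 / 77 / 77%.
- With equal 12% loss, power is 75.1 / 75.1 / 74.7% against 75.7 / 75.7 / 75.1%, a difference of at most 0.6 points.

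The mixed-model sizes and powers use a closed form with completers − 2 df. It was checked against direct REML in four data sets for estimates and standard errors, but not for the df that SPSS would use.

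**3. Do the documents show the condition?** The problem needs both missing T2 scores and the classical procedure.

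- Missing T2: the Methodology describes scores for each participant at each timepoint, for both outcomes. The SAP says that everyone randomized to begin an arm was included. No section reports a dropout, missing score or exclusion.
- Classical procedure: the Methodology's mixed-design label suggests it. The SAP's mixed-models label can mean a likelihood-based fit.

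The three statements (everyone included, two scores each, a T1–T2 ANOVA) are consistent with one another. Read as written, they describe a sound intention-to-treat analysis.

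**The case for a change.** The strongest reply is that the wording about each participant and each timepoint may only describe what the tests produce. It is not a count, and losing nobody over four weeks of training would be unusual. Mixed-design ANOVA is also the common name for the classical form. A method that supports the intention-to-treat claim whether or not T2 is complete seems preferable to one that supports it only if T2 is complete, and the simulated cases show no loss of precision from using it.

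Part of this stands. The documents do not prove completeness, and a reader would be helped by counts with T1 and T2 per arm for LDI and Items Recalled, and by the procedure name.

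The rest does not carry a change. Robustness to possible loss is an argument for a plan written before the data exist. Here the analysis is done, T2 completeness is already settled, and a model specified now would be post hoc. Nor does REML guarantee the claim:

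- It cannot include a participant with no score.
- It reduces the power loss without removing it (74–78% against 80%).
- It does not protect against loss that depends on the unobserved T2 score. In a smaller simulation of that case (300 runs, true effect 0.50, 10% and 20% missing), REML averaged 0.60 and 0.65 and the ANOVA 0.56 and 0.58.

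**Conclusion.** No change to the plan. The statistical mechanism is correct, but the documents do not show that it operated, and their plain reading is that it did not. If T2 was complete, or if the model was already likelihood-based on all available scores, a switch to REML gains nothing.

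The open details, T2 counts and procedure name, are ones that a results report normally supplies. If they showed that T2 was incomplete and the classical ANOVA was used, that result should be called complete-case, and a mixed model could be added as a disclosed post hoc analysis.

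The size in that event rests on assumed arm sizes, correlations, loss rates and a baseline-related mechanism in the VR arm only. The bias is 0.002 SD or less under equal 12% loss by the same mechanism, about 0.03–0.04 SD at 10% against 5%, and about 0.06–0.10 SD at 24% against 5%, never more than about a third of a standard error. The power cost in the most unequal case is larger, 10 to 14 points relative to the mixed model, but nothing in the documents suggests loss of that kind.

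### Both primary outcomes are tested by a valid but slope-fixed change-score comparison; a T1-adjusted estimate is usually more precise and should be added as a sensitivity analysis

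*Combined protocol and SAP*

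**What the plan says.** The Statistical Analysis Plan, which appears twice in the combined document in nearly the same words, describes one method: "Mixed models ANOVA were employed to examine the differences across the two conditions (Trackers and Control) between T1 (baseline) and T2 (post-training").

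The Methodology part of the Research Protocol Summary gives the model for each primary outcome. For the mnemonic discrimination score: "Mixed design ANOVA (repeated factors for time T1|T2 X between factors for condition Labyrinth-VR | Controls) was used for the analysis of LDI". For the WALK score: "Mixed design ANOVA (repeated factors for time T1|T2 X between factors for condition Labyrinth-VR | Controls) was used for the analysis of Items Recalled". T1 is therefore one of two response levels in both models. No baseline covariate appears anywhere, and the text does not say which ANOVA term is the treatment test.

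On numbers, the Design part says "Experiments enrolled 49 healthy older adults (mean 69 years of age) per protocol in a randomized controlled type interventional study" and "Outcome data were assessed at baseline (T1) and post-training timepoints (T2"). The Statistical Analysis Plan adds that "data from all participants randomized to begin a training arm were included in the analyses". The second copy ends by saying that "data were collected and analyzed only in the Experimental: LabyrinthVR Trackers and Placebo Comparator: Placebo Controls arms". The documents give no arm sizes, no count of participants with T2 data, no SDs, no T1-T2 correlation and no power calculation.

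**The concern.** With two timepoints, the time-by-condition interaction compares mean change between arms. Taking T2 minus T1 subtracts the whole of the baseline score, which is the best adjustment only if the true slope of T2 on T1 is 1. When the slope is lower, as regression to the mean usually makes it, the change score carries baseline noise that ANCOVA would remove. Only 49 people were enrolled and T1 is already collected, so the extra precision would need no new data.

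What is at stake depends on timing. If results by arm were still unseen, the gain would be power on the primary test. If they are known, as the past tense suggests, it is a narrower confidence interval on a supporting estimate, and the primary test gains no power.

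**Working it through.** There is no sample-size or detectable-effect figure in the plan to reproduce, so the check compares the two analyses.

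**Inputs from the documents.** N = 49 (Design); two arms and two timepoints; significance threshold 0.05 (Statistical Analysis Plan).

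**Assumptions.** All 49 have T1 and T2 and are in the two analysed arms, split 25/24; SDs and rho are the same in both arms; scores are normal; the test is two-sided; power is 80%. Effects are in T2 SD units. Rho and k = SD(T2)/SD(T1) are shown over a range.

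**Step 1: which test is it?** In a 2x2 mixed ANOVA the interaction F (1 and N-2 df) equals the squared t on T2 minus T1. A numerical example gave 8.1778 for both.

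**Step 2: validity.** In simulation at rho 0.6 with equal SDs, type I error was 5.1% for the interaction and 5.1% for ANCOVA.

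**Step 3: variances.**
- Change score: (1 + k² - 2·rho·k)/k²
- ANCOVA residual: 1 - rho²
- In raw units the difference is SD(T1)²·(1 - slope)², with slope = rho·k. It is never negative, so ANCOVA can lose only through having to estimate the slope.
- That cost, averaged over chance T1 imbalance, is 1 + 1/(N-4) = 46/45 = 1.022.

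**Step 4: detectable effect.** The noncentral t gives 2.8605 (47 df) and 2.8618 (46 df), and sqrt(1/25 + 1/24) = 0.2858.
- Change score: 2.8605 × 0.2858 = 0.817, times the square root of the change variance
- ANCOVA: 2.8618 × 0.2858 × sqrt(46/45) = 0.827, times sqrt(1 - rho²)

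Example with k = 1 and rho 0.5: the change variance is 1.00, giving 0.817. ANCOVA gives 0.827 × sqrt(0.75) = 0.716, which is 12.4% lower.

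| k | rho | Slope | Change score | ANCOVA | Reduction |
|---|---|---|---|---|---|
| 1 | 0.3 | 0.30 | 0.97 | 0.79 | 18.4% |
| 1 | 0.5 | 0.50 | 0.82 | 0.72 | 12.4% |
| 1 | 0.7 | 0.70 | 0.63 | 0.59 | 6.7% |
| 1 | 0.9 | 0.90 | 0.37 | 0.36 | 1.4% |
| 1.25 | 0.3 | 0.375 | 0.88 | 0.79 | 10.4% |
| 1.25 | 0.5 | 0.625 | 0.75 | 0.72 | 4.4% |
| 1.25 | 0.7 | 0.875 | 0.59 | 0.59 | -0.2% |
| 1.25 | 0.8 | 1.00 | 0.490 | 0.496 | -1.2% |
| 1.25 | 0.9 | 1.125 | 0.37 | 0.36 | 1.4% |
| 0.8 | 0.3 | 0.24 | 1.10 | 0.79 | 28.3% |
| 0.8 | 0.5 | 0.40 | 0.94 | 0.72 | 23.5% |
| 0.8 | 0.7 | 0.56 | 0.74 | 0.59 | 19.9% |
| 0.8 | 0.9 | 0.72 | 0.46 | 0.36 | 21.1% |

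**Step 5: CI width.** Taking the SDs as known, the 95% half-widths at k = 1 and rho 0.3, 0.5, 0.7 and 0.9 fall from 0.680 to 0.555, 0.575 to 0.504, 0.445 to 0.415, and 0.257 to 0.254. Simulated reductions in mean half-width were 18.4%, 12.4%, 6.8% and 1.4%.

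**Step 6: sensitivity.**
- A 30/19 split leaves the percentages unchanged.
- With 39 complete cases (20/19) and k = 1 they are 18.2%, 12.1%, 6.4% and 1.1%, and the average loss at slope 1 is 1.5%.
- The 1.2% loss is an average. At slope 1 and the 95th percentile of chance T1 imbalance it is about 4.3%: 1.0005 × sqrt(1 + 4.05/47) = 1.043.
- If slopes differ by arm, the bound need not hold. Take rho 0.5 and k = 1 in the larger arm, and rho 0.9 and k = 1.25 in the smaller. In simulation the ANCOVA estimate then had an SD 2.0% larger than the change score's at 30/19, but 1.2% smaller at 25/24. At 33/16 with rho 0.4 and 0.9 it was about 6% larger.

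**The case against.** The strongest reply is that this is a preference between two valid analyses, and that most of its benefit has gone. The model is clearly specified for both outcomes, and the text is retrospective throughout, including the statement that data had been collected and analysed in the two arms. Nothing in the documents supports the branch in which results by arm are unseen. Once they are seen, ANCOVA cannot decide anything. This stands, and it is why the recommendation is a supporting analysis.

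The reply can add that the size rests wholly on assumptions. The 28% end needs rho 0.3 together with a T2 SD 0.8 times the T1 SD, and neither has any support in the text. At rho 0.7 to 0.9 with SD ratio 1 or 1.25, the result runs only from a 1.2% loss to a 6.7% gain. This stands too.

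A reader might infer that ANCOVA can never cost more than about 1%. The documents do not support such a cap: it is an average over chance baseline imbalance and needs the same slope in both arms, while neither arm sizes nor slopes are given. The cases that break it are constructed, and with near-equal arms the problem largely disappears.

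What survives is the direction: for a common slope not close to 1, ANCOVA is more precise on average, and it uses data already in hand.

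**Conclusion.** The concern holds as an efficiency improvement. The documented interaction test is valid under randomisation but fixes the slope at 1. Under the assumptions listed above, the average gain from ANCOVA is material at low to moderate correlation and negligible at rho 0.9 with equal SDs. It turns into a loss of about 1% on average where the true slope is 1. That loss can be larger with chance T1 imbalance, or with unequal arms whose slopes differ. Where this trial falls in the range cannot be told from the documents.

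Two stronger readings should be resisted. One is that the ANOVA is wrong or biased; randomisation and the simulated error rates say otherwise. The other is that the trial's primary test would gain power from a switch now. At a true difference of 0.7 SD, equal SDs and rho 0.5, power would be 0.782 rather than 0.670, but only if ANCOVA had been fixed as the deciding test before results by arm were known.

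**What to change.** Name the time-by-condition interaction as the deciding test for each primary outcome. Add, for each, an ANCOVA of T2 score on condition with that outcome's T1 score as covariate. Report the adjusted difference with its 95% CI as a sensitivity analysis labelled post hoc. Only if results by arm are in fact unseen should ANCOVA become the primary test, with the interaction as supporting.

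In either case report rho, the T1 and T2 SDs and the number with both scores, by arm, so that readers can judge how much the choice matters.

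The cost is one extra model per outcome in the same software and one degree of freedom, with no new data. The caution is that running both tests and reporting the better one would raise type I error to about 6-8% in simulation with equal SDs, so the deciding test has to be stated.

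### Does the silence on how the expectancy survey was scored and used leave the claim about training unsupported?

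*Combined protocol and SAP*

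**What the plan says.** The survey appears once, under Design in the Research Protocol Summary: "After orientation to their respective treatment games, all participants completed an expectancy survey regarding how their treatment would affect cognitive performance". The sentence gives who completed it, when, and what it asked about. It names no instrument, scale or score.

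The same section describes the comparison: "The two treatment arms were Labyrinth VR training versus placebo control narrative games played on an iPad tablet computer". Under Methodology the control is "four commercially available narrative computer games as placebo controls", and either arm involves roughly 12 hours of play spread over four weeks.

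Under Goals the aim reads: "The primary objective is to show training-induced gains in high-fidelity LTM".

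The stated analysis is the same throughout. For the discrimination score, "Mixed design ANOVA (repeated factors for time T1|T2 X between factors for condition Labyrinth-VR | Controls) was used for the analysis of LDI", and the WALK paragraph gives the same model for Items Recalled. Both copies of the Statistical Analysis Plan describe a mixed ANOVA of two conditions across T1 and T2. None of these places contains an expectancy term or an expectancy comparison.

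**The concern.** A participant wearing a VR headset and one playing story games on a tablet can both see what they were given, and may hope for different things from it. If expectations differ by arm and also influence memory scores, part of an arm difference could reflect expectation rather than training. The objective is worded causally, as gains induced by training. The sponsor collected the one measure that could describe expectation by arm, and the documents state no use for it. They also do not say that participants were blinded or that expectations were similar in the two arms.

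What would be at stake is the interpretation of a positive result. The validity of the test would not be affected.

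**Working it through.** **Step 1: what is absent.** The whole text contains one mention of the survey. No scoring, between-arm comparison, covariate or sensitivity analysis of expectancy is stated. The documents give no power calculation, effect size or SD, so there is no planned figure to reproduce.

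**Step 2: what the silence affects.** The primary analysis is the time-by-condition contrast for each outcome. Expectancy is not an input to it, so the estimate, its standard error and the p-value are the same whether or not the survey is analysed.

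**Step 3: what support for attribution the documents do state.** Participants were randomised, the comparator is a placebo game arm, and play time is about the same in both arms. That protects against practice with devices, contact time and general engagement. It does not prove equal expectation, but the training claim is not left without support.

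The plan's phrase that each outcome "was considered as a potential measure of generalization of training effects in its own right" does not bear on this question. The Methodology paragraphs use generalization for transfer from the game to untrained memory tasks, and make no contrast between training and expectation.

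**Step 4: what an analysis of the survey could deliver.** From the documents: 49 participants. Assumed: every participant has a score, and the split is 25/24 or, as an uneven case, 33/16 (the documents give no split). With 47 degrees of freedom the two-sided 5% critical t is 2.012.

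- Standard error of the difference, in SD units: √(1/n₁ + 1/n₂). At 25/24, √(1/25 + 1/24) = 0.286. At 33/16, √(1/33 + 1/16) = 0.305.
- 95% half-width, 2.012 × standard error (unrounded): 0.575 SD at 25/24 and 0.613 SD at 33/16.
- Power (noncentral t, non-centrality = gap / standard error):

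| True expectancy gap (SD) | 25/24 | 33/16 |
|---|---|---|
| 0.3 | 17.7% | 16.2% |
| 0.5 | 40.3% | 36.3% |
| 0.8 | 78.3% | 73.0% |

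- Gap needed for 80% power: 0.817 SD at 25/24 and 0.871 SD at 33/16.

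A non-significant comparison would therefore not show equal expectations, and a moderate gap would usually remain possible.

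**Step 5: could adjustment settle it?** The survey followed orientation to the assigned game, so the score is a post-allocation variable. An ANOVA adjusted for it conditions on something the assignment may have changed, and its condition effect is no longer the randomised contrast. It would also cost precision. Before any gain from explained variance, the condition standard error is multiplied by √(1 + gap² × n₁n₂/49²). At 25/24 this is 1.011 for a gap of 0.3 SD and √(1 + 0.64 × 600/2401) = 1.077 for a gap of 0.8 SD.

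**Step 6: can the share due to expectation be sized?** Not from these documents. The expectancy contribution is gap × slope, compared with a chosen outcome difference. Take 25/24, a T1–T2 correlation of 0.5, and a just-significant change difference of 2.012 × √(2 × 0.5) × 0.286 = 0.575 SD. Then a gap of 0.3 with slope 0.1 gives 0.03/0.575 = 5%, and a gap of 0.8 with slope 0.3 gives 0.24/0.575 = 42%. Every input except the 49 is assumed. The benchmark is the smallest significant effect, which makes the share as large as it can be among significant results. With an effect 1.5 times larger (0.862 SD) the range falls to 3% to 28%. With no gap or no slope it is zero, and a gap favouring control would reverse its sign. These percentages restate the assumptions and are not evidence of bias in this trial.

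**The case for a change.** The strongest case for acting is that matched hours and a placebo label do not establish matched expectation. The survey is the only data mentioned that could inform the point, and reporting it would take about one sentence on scoring and one table row, on data already collected. An interval by arm would let readers judge how far the causal wording is justified.

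Most of this stands as a description. The absence is real, the cost is small, and no passage says that expectations were similar.

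What does not stand is the step from there to a fault in the plan. The survey cannot separate training from expectation, so leaving it out is not the reason that question stays open. The summary is also very brief: it gives no scoring formula for its two primary outcomes, so silence about a survey it does not name as an outcome says little about what was done with it. The text is written in the past tense and reports analyses already carried out, so an added comparison would be post hoc unless an earlier dated plan specified it.

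**Conclusion.** No change to the plan is called for. This is missing detail whose addition would alter no estimate, p-value or error rate, and would not resolve the question that prompts it. Attribution to training rests on randomisation and a placebo arm with about the same play time. That support is real but incomplete, and the survey would leave it incomplete.

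The sizes that matter are the precision figures: a half-width of about 0.6 SD and power of 36% to 40% for a 0.5 SD gap. They rest on the stated 49 participants, complete surveys and an assumed split between 25/24 and 33/16. No estimate of the share due to expectation can be drawn from the documents.

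Authors who wish to help readers may describe the score and show expectancy by arm with the difference and its 95% interval. They should label it post hoc unless it was pre-specified, and note that non-significance does not mean equality. That is optional reporting, and the primary ANOVA stays as it is.

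### Does the switch from WALK to TOUR between the two SAP copies leave the second primary outcome undefined?

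*Combined protocol and SAP*

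**What the plan says.** The combined document contains a Statistical Analysis Plan, then a Research Protocol Summary, then a second Statistical Analysis Plan. Both SAP copies carry the same trial title, identifier and date ("December 8, 2022").

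- **SAP, first copy:** "Therefore, the analyses of LDI scores and WALK scores were independent of each other".
- **SAP, second copy:** "Therefore, the analyses of LDI scores and TOUR scores were independent of each other". This copy also closes with a sentence saying that, for funding reasons, only the Trackers and placebo control arms were collected and analysed.
- **Research Protocol Summary, Design:** "the primary outcome measures assessed two capabilities for high-fidelity LTM retrieval".
- **Research Protocol Summary, Methodology:** "MDT was one primary outcome measure and provided an LDI score for each participant at each timepoint"; and "WALK was another primary outcome measure and provided an Items Recalled score for each participant at each timepoint". Each measure is given a mixed ANOVA with time (T1, T2) as the repeated factor and condition as the between factor.

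The name TOUR occurs once in the whole file, in the second SAP copy.

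**The concern.** The sentence that changes is the only one in either SAP copy that names the outcomes. One copy says WALK and the other says TOUR. They share a date, and nothing says that the names mean one task or which copy governs. Because the second copy has the extra sentence on arms, a reader may take it as the later one and conclude that WALK was dropped in favour of an undefined measure.

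If the two names were two tasks, there would be two risks: a primary outcome might go unanalysed, or a third memory measure might be available from which to pick a favourable result. The texts are written in the past tense, each measure is treated as evidence in its own right, and no multiplicity adjustment is stated. A fixed list of outcomes is then the main protection against selective reporting, so doubt about that list deserves a check.

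**Working it through.** The documents give no sample size calculation, effect size or power, so there is no figure of the plan's own to reproduce. The check is mainly a comparison of texts.

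**1. What differs between the SAP copies.** Apart from layout, two things differ: the outcome name (WALK or TOUR) and the closing sentence on arms. The intent-to-treat rule, the mixed ANOVA, the software and the 0.05 threshold are the same.

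**2. What the differing sentence does.** It states that two analyses were separate from each other. It does not list endpoints, define a score or label anything primary. That label comes only from the Research Protocol Summary.

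**3. Where the second primary outcome is defined.**

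| Element | WALK | TOUR |
|---|---|---|
| Called primary | Yes (Summary, Methodology) | No |
| Score | Items Recalled | None given |
| Construct | Recent autobiographical memory | None given |
| Timepoints | T1 and T2 | None given |
| Model | Mixed ANOVA, time by condition | None given |

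Only one candidate has a definition.

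**4. How many outcomes there are.** The Summary counts two capabilities and names two measures. Each SAP copy also names two: LDI and one other. A single task under two names fits this count. A third outcome would need some place to list three, and none does.

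**5. Whether the second copy is later and removes WALK.** The dates are equal and there is no version number. The closing sentence does not settle the order, because the first copy already compares only Trackers and Control. The ANOVA paragraph names no outcome in either copy, so the second copy does not withdraw the Items Recalled analysis that the Summary specifies.

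**6. Size if a third test did exist.** Inputs: a threshold of 0.05 per test (both SAP copies) and independent tests (an assumption made here).

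- Two tests: 1 − 0.95² = 0.0975.
- Three tests: 1 − 0.95³ = 0.1426.
- Increment: 0.1426 − 0.0975 = 0.0451, about 4.5 percentage points.
- Limit for three tests without the independence assumption: 3 × 0.05 = 0.15.

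The 9.75% applies whichever name is used, so it is a matter of multiplicity across two primaries and not of this naming question. Only the 4.5 points would belong here, and only if TOUR is a separate measure that was tested.

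**The case for a change.** The strongest opposing case is that the documents cannot prove the two names mean one task. The SAP says that each measure has its own procedure, stimuli and metric, so two names can be read as two measures. A wrong outcome name in a SAP is also more serious than a slip in background text, and only the sponsor can say what TOUR is.

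Part of this stands. The mismatch is certain, TOUR is undefined, and nothing reconciles the names or ranks the copies. The step from there to an undefined primary outcome does not stand, because WALK is fully specified in the same file and the first SAP copy agrees with it.

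The remedy for the two-task case also has little to offer. The texts describe analyses already done, so classing TOUR as secondary now would be a post hoc label with no basis in the documents. It would not restore any protection that a fixed list of outcomes should have given beforehand.

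**Conclusion.** This is a clerical inconsistency in one word, and the plan needs no change. Followed as written, it analyses LDI and WALK Items Recalled, each by a time-by-condition mixed ANOVA at 0.05. Using one name throughout would be tidier but would alter no estimate, test or conclusion.

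This rests on reading the Research Protocol Summary as the definition of the primary outcomes, which is the only definition in the file, and on there being no third tested measure, which no text reports. Under that reading the effect on results is zero. The 4.5-point rise in family-wise error is hypothetical: it needs a separate TOUR test and independence between tests. Evidence that TOUR was a distinct task, analysed alongside or in place of WALK, would reopen the question; the documents contain none.
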